I understand that if this study involves use of UC Davis students' educational records (including records in the PI's own possession such as course exams/assignments), I must consult with the Registrar's office to see if all requirements of the Family Educational Rights and Privacy Act (FERPA) are satisfied.

Data Analysis & Statistical Considerations:

PROTOCOL TITLE: Evaluation of Software Generated Customized Foot Orthoses

A quasi-experimental, within-subject (repeated measures) and longitudinal controlled design will be established. Patients will be recruited from the patient population at the University of California, Davis Orthopaedic Foot and Ankle Clinic. From the total number of enrolled subjects who meet the inclusion criteria, an optimal N of 52 subjects will be randomly selected, considering a medium effect size (0.4) and a p less than 0.05 to achieve a statistical power of 0.8. Being a longitudinal study, a sample loss of 10% was established. Therefore, 60 subjects will be included in the study. We aim to enroll up to 60 participants over the course of 1-3 months.

Intra-subject pain, comfort, and quality of life averages pre-use and post use of the foot orthoses will be compared. The sample of participants will be described with central tendency statistics and baseline parameters, and post use evaluations (0, 7, and 30, 120, and 360 days after first foot orthoses use) will be established. These will be compared to study possible differences. For normally distributed dataions, repeated measures, one-way ANOVA for paired samples will be used for normal distributions will be used with a Tukey's post-test and in case of non-normal distributions, Friedman's test will be used with a Dunn's post-test. All analyses will be performed with the SPSS statistical package.

Privacy, Data Storage & Confidentiality:

All study data, such as forms, reports, and other records, including electronic records, will be identified by a coded number to maintain patient confidentiality and will only be accessible by members of the research team. Paper records will be kept in locked file cabinets in locked rooms. Electronic data will be located on computers containing a log-on and password. Written permission from the participant must be obtained prior to the release of clinical information, except as necessary for monitoring by the IRB. All communication, consent procedures, forms, and storage of patient data will be maintained and stored in accordance with the UC Davis' IRB, Good Clinical Practices requirements, and the Health Insurance Portability and Accountability Act. All personnel involved with the study are required to complete the Protection of Human Subjects training.

Due to the complexity of the software, it will only be used by a trained kinesiologist belonging to the Soleit team.

Although the evaluating kinesiologist will have access to all the volunteers' data temporarily in order to carry out the correct control and follow-up work, three independent databases will be maintained to guarantee the confidentiality of the information:

- a. Identification data: Data allowing identification of patients will be kept in Excel listing, handled by the study investigators.

PROTOCOL TITLE: Evaluation of Software Generated Customized Foot Orthoses

- b. Biomechanical data: The data corresponding to pressure measurements, medical history and images are essential for the automated design of the foot orthoses and will be managed anonymously, without any participant identifiers, in the Soleit software.
- c. Tracking Data: Tracking forms for recording the effectiveness of the foot orthoses will be managed independently via surveymonkey.com and will be anonymously transmitted, without any participant identifiers, to the principal investigator after which the surveymonkey.com service will be cancelled, and the data deleted.

At the end of the evaluation, all data will be anonymized and delivered to the researcher responsible for statistical analysis.

8) Data and/or Specimen Banking

Address the last bullet point if you answered “Yes” to tissue banking within the Initial Application Form.

If data will be banked for future uses address the following questions:

- *What data will be banked?*
- *What identifiers will be included in that data?*
- *For what purpose will the data be used?*
- *Where and how will data be stored?*
- *How long will the data be stored?*
- *Describe the procedures to release data, including: the process to request a release, approvals required for release, who can obtain data or specimens, and the data to be provided with specimens.*

9) Provisions to Monitor the Data to Ensure the Safety of Subjects

As this is a minimal risk study, no data and safety monitoring (DSMB) will be used. Microsoft Excel will be used to manage data used. Sponsor will conduct an ongoing monitoring of study conduct and safety data.

The following will be reported within 10 calendar days, except when 24-hour reporting is specified:

1. Information that indicates a change to the risks of potential benefits of the human research:
 - a. An interim analysis, safety monitoring report, publication in the literature, or revised investigator brochure that indicates an increase in the frequency or magnitude of a given harm, uncovers a new risk, or provides more information about the benefits of the human research.
 - b. Change in FDA labeling or withdrawal of the device from the market.
 - c. Protocol deviation that harmed participants or indicates participants might be at increased risk of harm. If the protocol deviation was made in

PROTOCOL TITLE: Evaluation of Software Generated Customized Foot Orthoses

order to eliminate an apparent immediate hazard to a participant, the PI must submit the information within 24 hours.

d. Complaint of a participant that indicates participants or others might be at increased risk of harm or at risk of a new harm.

2. Any adverse event experienced by a participant or other individual, which is both unexpected and at least probably related to the human research device.

a. A harm is “unexpected” when its specificity and severity are not accurately reflected in the consent document.

b. A harm is “at least probably related” if the research device more likely than not caused the harm.

c. Timeline Exception: If the unexpected and at least probably related harm is death of a research subject, the PI must report the information within 24 hours.

3. Finding of Non-Compliance or Allegation of Non-Compliance.

4. Protocol Deviations: Failure to follow the protocol due to the action or inaction of the investigator or research staff. Exception – If the protocol deviation was taken in order to eliminate an apparent immediate hazard to a participant, the PI must report the information within 24 hours.

5. Breach of confidentiality: must be reported within 24 hours.

6. Change to protocol taken without prior IRB review to eliminate an apparent immediate hazard to a participant: must be reported within 24 hours.

7. Complaint of a participant that cannot be resolved by the research team.

8. Unanticipated adverse device effect. Exception – if the unexpected and at least probably related adverse device effect results in the death of a research subject, the PI must report the information within 24 hours.

All data collected will remain confidential. Data will be stored securely under the patient’s study identification number. All clinical data, images and surgical/procedural data will be de-identified prior to any in-house or public presentation of data or images. Coded data will only be released to those listed as study investigators or support staff. Paper data records will be stored in locked file cabinets in a locked office. All electronic research data will be stored on the PI computer that is password protected and encrypted.

IRB, FDA and any applicable regulatory agencies will have access to the study records upon request. The data and associated identifiers will be kept for up to 5 years in a locked research facility accessible only to designated personnel, at which time the data will be destroyed per hospital policy. If the results of this study are published, the data will be reported

PROTOCOL TITLE: Evaluation of Software Generated Customized Foot Orthoses

collectively without mention of any subject's identity, thereby ensuring subject anonymity.

10) Withdrawal of Subjects

Subjects may withdraw from the study at any time. Subjects may be withdrawn by an investigator if the participant does not participate in study follow-ups. Research staff will document the reason for withdrawal. Subjects who fail to appear at initial visit or do not receive the foot orthoses will be considered screen failures and will be removed from the study and the study data.

11) Risks to Subjects

Risk Assessment and Device-Related Risks:

Discomfort:

A conceived device-related risk is that the foot orthoses cause discomfort. This will be controlled in two ways. The first is that the use of the foot orthoses will be done progressively. This means that participants should use the foot orthoses for 1 hour on the first day, then increase use by 1 hour each day until reaching 4 consecutive hours at which time the foot orthoses can be worn continuously. Any discomfort should be reported to the nurse practitioner in charge and will be reviewed to assess if a new foot orthosis with the appropriate modifications should be made or if the use of the foot orthoses should be discontinued.

Blisters:

Another conceived device-related risk is the generation of blisters due to friction. If a participant is found to experience an area of increased rubbing that could lead to a blister, the participant should discontinue the use of the foot orthoses immediately. In addition, as a part of protocol, participants should inspect the soles of their feet when they finish any type of physical activity and check for any areas of redness as a result of the use of the foot orthoses. If any redness is present, inform the nurse practitioner who will assess if new foot orthoses with the appropriate modifications should be made or if the use of the foot orthoses should be discontinued.

12) Potential Benefits to Subjects

Participants will receive custom-made foot orthoses free of charge. No additional compensation will be received.

13) Sharing of Results with Subjects

N/A Results will not be shared with patients.

14) Provisions to Protect the Privacy Interests of Subjects

As part of the consent process, the patients will be informed about the nature of the data that will be collected, how the information will be collected and who will have access to the information and how it will be stored. The information will be handled initially by the clinical and research team at the collecting institution and only shared with the data hub institution UC Davis in a deidentified format.

15) Economic Burden to Subjects

The only anticipated cost is transportation to the clinic during the initial visit. There will be no cost to the subjects for the manufacturing of the foot orthoses. The non-standard of care foot orthoses will be paid for by Soleit.

16) Drugs or Devices

If the research involves drugs or device, describe your plans to store, handle, and administer those drugs or devices so that they will be used only on subjects and be used only by authorized investigators. N/A

- I confirm that all investigational drugs will be received by the Investigational Drug Service (IDS). The IDS will store, handle, and administer those drugs so that they will be used only on subjects and be used only by authorized investigators.
- I confirm that all investigational devices will be labelled in accordance with FDA regulations and stored and dispensed in such a manner that they will be used only on subjects and be used only by authorized investigators.

17) Review Requirements

Are there any contractual obligations or other considerations that require IRB review of this research, or review at intervals other than those required by the Common Rule or FDA? If yes, check box:

Yes

No

References:

1. Tran K, Spry C. Custom-Made Foot Orthoses versus Prefabricated foot Orthoses: A Review of Clinical Effectiveness and Cost-Effectiveness [Internet]. Ottawa (ON):

PROTOCOL TITLE: Evaluation of Software Generated Customized Foot Orthoses

Canadian Agency for Drugs and Technologies in Health; 2019 Sep 23. Available from: <https://www.ncbi.nlm.nih.gov/books/NBK549527/>

2. A.G. Lucas-Cuevas, P. Pérez-Soriano, J.I. Priego-Quesada & S. Llana-Belloch (2014) Influence of foot orthosis customisation on perceived comfort during running, *Ergonomics*, 57:10, 1590-1596, DOI: 10.1080/00140139.2014.938129
3. Fuller, Joel & Bellenger, Clint & Thewlis, Dominic & Tsilos, Margarita & Buckley, Jonathan. (2014). The Effect of Footwear on Running Performance and Running Economy in Distance Runners. *Sports Medicine*. 45. 10.1007/s40279-014-0283-6.

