off painful areas in patients with intermetatarsal bursitis, reducing pain and disability, which was supported by ultrasound findings [15].

The literature has been consistent in pointing out the positive effects of foot orthoses on comfort in the short term. For example, studies such as that of Tarrade et al [16] found significant improvements in the pain of workers who remained standing for long periods of time when using foot orthoses. However, the medium to long term evidence for this is still not very clear. Among the scarce evidence on this subject, García-Hernández et al. [17] demonstrated that manufacturing workers showed greater comfort after a period of adaptation, which occurred between one and two months after starting the use of foot orthoses. Carrying out this process, using modern, tailor-made manufacturing systems could mean better results, as these methods have proven to be the most effective in generating foot orthoses.

Though the shape of people's feet varies from person to person, currently typical shoes have inside standard foot orthoses that do not provide customized designs to fit the differences in shape of the foot of each person who uses them. This generates a wide range of loading and pressure distribution along the sole. This can generate pain and a reduced quality of life in the people who use them. Today we have the possibility of designing foot orthoses tailored to each person's foot, which generates a support and impacts absorption according to the shape of one's foot, which would allow us to generate greater comfort and thus avoid discomfort and injuries caused by the alteration of the loads. The goal of this study is to find out whether the use of software generated custom-made orthopedic foot orthoses improves pain in the long term.

3) Inclusion and Exclusion Criteria

The attending orthopaedic foot and ankle surgeons will identify patients based on clinical exam and/or radiographic findings. Screening and eligibility will be conducted by the research coordinator.

Inclusion Criteria:

1. Foot/ankle pain or pathology OR diagnosed pes planus, pes cavus, pronator foot, supinator foot, metatarsalgia, Morton's neuroma, sesamoiditis, hallux valgus, intermetatarsal bursitis.
2. Between 18 and 65 years of age
3. BMI is greater than 18.5 or less than 30.

Exclusion Criteria:

1. Individuals who have had surgery in the lower limbs during this past year.
2. Individuals who already have custom-made orthopedic orthoses.

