3. Patients with active diabetic ulcers or chronic foot pressure ulcers.

4) Study Timelines

We aim to enroll up to 60 participants over the course of 1-3 months. Each participant will be evaluated at baseline, when the customized foot

PROTOCOL TITLE: Evaluation of Software Generated Customized Foot Orthoses

orthoses will be made, and the corresponding tests will be conducted. Subsequently, consecutive surveys will be carried out at 0, 7, 30, 120, and 360 days. days from the first day of foot orthoses use to measure the change in pain and comfort with use of the foot orthoses. An interim analysis will be conducted after all subjects have completed the 30-day time point. This interim analysis will allow us to determine whether subjects are using the foot orthoses they have been provided. Complete primary analyses is estimated to be completed within 3 months after the termination of the study.

5) Study Endpoints

Primary endpoint: Successful patient use of a 3D printed custom orthotic for at least 6 months and up to 1 year

6) Secondary endpoint: Improvement in patient report outcomes after the use of a 3D printed custom orthoticProcedures Involved

The evaluation will have a duration of approximately 30 minutes, which consists of four stages:

- a. Collection of personal data and anamnesis: The patient's demographic data, anthropometric measurements and anamnesis will be consulted.
- b. Physical examination: Visual and palpitory inspection of the foot.
- c. Baropodometry: Taking of plantar pressures by means of a platform.
 - i. Static: Subjects should remain standing on the platform measuring plantar pressures for 15 seconds with arms at the sides and looking straight ahead. There is only 1 sample.
 - ii. Dynamic:
 1. Walking: Subjects should walk over the pressure measurement platform. Five shots per foot, with a protocol of 5 steps to reach the platform.
- d. Hindfoot photography: A photograph of the hindfoot will be taken, which allows us to measure the angulation of the hindfoot.

Making and Delivery of Foot Orthoses:

During a period of 2 weeks, the foot orthoses will be created using Soleit software which will later be manufactured via three-dimensional printing.

Use of Foot Orthoses:

Foot orthoses will be sent to participants along with a small instruction manual and protocol of use. When using the foot orthoses for the first

PROTOCOL TITLE: Evaluation of Software Generated Customized Foot Orthoses

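### The sample-size paragraph says 52 enrolled subjects will be randomly selected yet 60 included, and its 80% power fits one unadjusted paired comparison, not the planned Tukey pairwise tests

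*Protocol*

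**What the plan says.** Protocol section 7 (Data Analysis & Statistical Considerations) describes one group: "A quasi-experimental, within-subject (repeated measures) and longitudinal controlled design will be established". The draw is made among eligible people already enrolled, and the sentence reads: "an optimal N of 52 subjects will be randomly selected, considering a medium effect size (0.4) and a p less than 0.05". The power sought is 0.8. It continues: "Being a longitudinal study, a sample loss of 10% was established. Therefore, 60 subjects will be included in the study". Sections 4 and 7 both set the ceiling: "We aim to enroll up to 60 participants over the course of 1-3 months".

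The next paragraph of section 7 gives the analysis: "Intra-subject pain, comfort, and quality of life averages pre-use and post use of the foot orthoses will be compared". The method is "repeated measures, one-way ANOVA for paired samples will be used for normal distributions", with a Tukey post-test, or Friedman's test with a Dunn post-test if the data are not normal. The times are days 0, 7, 30, 120 and 360, plus baseline parameters, so five or six levels.

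The power sentence does not say which effect-size index 0.4 is, or which outcome, time point or test it concerns. Section 1 gives pain reduction as the purpose, and section 2 gives the goal as whether the orthoses "improves pain in the long term". Section 5 makes successful use of the orthotic the primary endpoint and patient-reported outcomes secondary.

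**The concern.** There are two separate problems in one paragraph.

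The first is who is studied. Enrolment stops at 60 and 60 are included, so 52 cannot also be drawn at random from those enrolled. Every subject receives the same intervention and is compared with himself or herself, so a random draw does nothing for allocation. Its only effect would be to leave out people who had consented and been given orthoses.

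The second is what the 80% refers to. A reader of section 7 will attach it to the analysis described in the next paragraph, which covers several time points with adjusted pairwise tests. If 52 was computed for one unadjusted paired comparison, a non-significant pairwise result would be read as coming from a test with 80% power when its actual power is well below that.

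**Working it through.** **Inputs from section 7:** effect size 0.4, p below 0.05, power 0.8, 52 subjects, 10% loss, 60 included, five or six times. **Assumptions, not in the protocol:** two-sided testing; 0.4 is dz, the mean paired difference divided by the SD of the differences; equal variances and correlations over time (sphericity).

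**1. Reproducing 52.** Paired t-test with df = n − 1, noncentrality 0.4 × √n, two-sided 0.05:
- n = 51: power 0.7999
- n = 52: power 0.8078

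So 52 is exactly the smallest n. A one-sided test would need 41.

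**2. Other readings of 0.4.**
- Cohen's f in the planned repeated-measures ANOVA, noncentrality f² × n × K/(1 − ρ): 6 to 17 subjects for K = 5 or 6 times and correlation ρ from 0 to 0.7. A different convention for f gives 19 to 21. None is near 52.
- Raw-score SD units, dz = 0.4/√(2(1 − ρ)): 71, 52 or 32 subjects at ρ = 0.3, 0.5 or 0.7. The value 52 appears only at ρ = 0.5, where the two definitions coincide.
- Two independent groups with f = 0.4 also give 52 in total, but this trial has no second group.

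Within this one-group design, the paired reading is the one that produces the stated number.

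**3. Reproducing 60.** 52/0.9 = 57.8, so 58 would do. With 60 enrolled, 60 × 0.9 = 54 completers remain.

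**4. Effect of the selection rule** (paired test, dz = 0.4):

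| Reading | Subjects dropped | Analysed | Power |
|---|---|---|---|
| No selection | 0 | 54 | 0.823 |
| 52 drawn from 54 completers | 54 − 52 = 2 | 52 | 0.808 |
| 52 drawn from 60 at the start, then 10% lost | 60 − 52 = 8 | 52 × 0.9 = 46.8, about 47 | 0.766 |

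**5. One specified pair under Tukey.** Critical value q/√2 with df = (n − 1)(K − 1), noncentrality 0.4 × √n:

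| Times | n | Critical value | Power |
|---|---|---|---|
| 5 | 52 | 2.752 | 0.553 |
| 5 | 54 | 2.751 | 0.575 |
| 6 | 52 | 2.872 | 0.506 |
| 6 | 54 | 2.871 | 0.528 |

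**6. Omnibus F.** If the largest difference between times equals dz = 0.4, the noncentrality is 2 × n × 0.4² × S. Here S is the sum of squared deviations of the time means, scaled so that the largest difference is 1.
- Change confined to the first or the last time: S = 0.8 (five times) or 0.833 (six). Power is 0.837 and 0.825 at n = 52, and 0.853 and 0.842 at n = 54.
- Gradual linear change: S = 0.625 or 0.7. Power is 0.724 and 0.743 at n = 52, and 0.743 and 0.762 at n = 54.
- A step after day 0 with six times: S = 1.333. Power is 0.967 at n = 52.

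The Friedman/Dunn branch was not calculated.

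**The case against.** The random selection is probably loose language that nobody would carry out. The next sentences raise 52 to 60. Section 4 evaluates each participant, and its interim analysis waits for all subjects to reach day 30. Section 10 removes only those who miss the initial visit or "do not receive the foot orthoses will be considered screen failures and will be removed from the study and the study data". No other section describes a draw. This is a fair account of the intent, and it is why the case of 47 left is the less likely one: it applies the 10% loss after the selection, whereas section 7 uses that loss to get from 52 to 60. It does not rescue the sentence, which still states a rule that conflicts with the following one.

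On power, the protocol never attaches 0.8 to a Tukey pair, and an intra-subject comparison of pre-use with post-use fits a paired test. That is also fair. A reader might infer that the 80% cannot be checked at all; that goes too far, since 52 can be recovered exactly. A reader might also use the raw-SD or f readings to argue that the true power is anywhere from poor to ample. Away from ρ = 0.5 those readings do not yield 52, so they are weak evidence of what was meant. What stands is that the recovered test is not named in the analysis paragraph, and the tests that are named there do not all have the stated power.

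**Conclusion.** The point holds as an internal inconsistency together with a power statement that is not tied to its test. It should be fixed, but it does not threaten the trial.

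The protocol does not support saying that 52 or 60 is wrong, or that the trial is underpowered: 54 completers give 0.82 for the comparison that 52 evidently came from. Nor does it support saying that the selection rule will take power below 0.8. On the likelier literal reading the cost is 2 subjects and power moves from 0.82 to 0.81; only selection at the start gives 0.77.

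The 0.8 does not extend to the planned pairwise tests, which have about 0.51 to 0.58 for one specified Tukey pair. For the omnibus F it depends on the pattern: about 0.72 to 0.85 if the change is gradual or confined to the first or last time, and higher for other patterns. These figures rest on two-sided testing, sphericity, 52 to 54 completers and 0.4 as the paired standardised difference. That last definition is inferred from the match at 52 and is not stated in the protocol.

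The 0.8 is also not power for the section 5 primary endpoint, which is use of the orthotic and not a mean change.

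**What to change.** In section 7:

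1. Delete the random selection. State that all enrolled subjects who receive orthoses (up to 60) are analysed, with 52 as the target number of completers. This agrees with the screen-failure rule in section 10.
2. Define 0.4 as the mean paired difference divided by the SD of the differences. If something else was meant, name the index and any assumed correlation.
3. Tie the 80% to one named pre-use versus post-use pain comparison at two-sided 0.05. Day 360 would suit the long-term goal in section 2, but the time point is the sponsor's choice.
4. State that this is not the power for the orthotic-use primary endpoint in section 5, and reconcile that endpoint with the pain purpose in section 1.
5. Confirm that a pain score is taken before first use. The four baseline stages in section 6 list none, and the surveys start at day 0.
6. Report the other pairwise comparisons as multiplicity-adjusted secondary comparisons, with stated power of about 0.5 to 0.6 at 0.4.

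N does not change. Most of this is rewording, but it places one comparison ahead of the others and gives a less favourable stated power for the post-tests. If no pre-use pain score is currently planned, item 5 would add one short assessment. Sizing for a Tukey pair instead would take 81 completers (five times) or 86 (six), and is not proposed.

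### Tukey's test after repeated-measures ANOVA normally uses one pooled error, which misstates precision by visit pair if correlation falls over gaps of 7 to 360 days

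*Protocol*

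**What the plan says.** Section 4 (Study Timelines) sets the schedule: "consecutive surveys will be carried out at 0, 7, 30, 120, and 360 days". The Data Analysis & Statistical Considerations text in section 7 repeats it: "post use evaluations (0, 7, and 30, 120, and 360 days after first foot orthoses use) will be established". For normal data it names "repeated measures, one-way ANOVA for paired samples will be used for normal distributions", and the sentence goes on: "will be used with a Tukey's post-test and in case of non-normal distributions, Friedman's test will be used with a Dunn's post-test". The software is named ("All analyses will be performed with the SPSS statistical package"). The text does not mention sphericity, an error term for the post-test or a covariance structure, and it gives no standard deviation or between-visit correlation.

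The background (section 2) gives the aim as finding out whether "software generated custom-made orthopedic foot orthoses improves pain in the long term". The sample size is "an optimal N of 52 subjects will be randomly selected, considering a medium effect size (0.4) and a p less than 0.05", with target power 0.8.

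**The concern.** The classical Tukey comparison after a one-way repeated-measures ANOVA divides every pairwise mean difference by the same standard error, built from the subject-by-time mean square. That standard error is right for every pair only if all pairwise differences share one variance (sphericity). Here the gaps between visits run from 7 to 360 days. Scores a week apart would usually correlate more strongly than scores a year apart. If they do, the pooled error is too small for the widest gap and too large for the shortest. The long-term pain comparison would then be reported with too much confidence, and the first-week comparison with too little. An epsilon correction to the overall F test would not repair this, because it leaves the pooled post-test error unchanged.

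**Working it through.** **The plan's own figure.** A two-sided paired t-test with standardized difference 0.4, alpha 0.05 and n = 52 has power 0.808, so 52 reproduces as the size for one paired comparison. I use n = 52 below.

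**Inputs from the protocol.** Five visits (0, 7, 30, 120, 360 days), n = 52, Tukey at 5%. Error degrees of freedom are 51 × 4 = 204. The critical value is q(5, 204) = 3.892, or 3.892/√2 = 2.752 on the t scale, which is about 0.6% per pair when sphericity holds.

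**Inputs assumed.** Correlations, because the protocol gives none; also normal scores, no missing data and, except in the counter-case, equal SDs at all visits.
- Log pattern: correlation falls from a to b as r(g) = a − (a − b) × ln(g/7)/ln(360/7), where g is the gap in days.
- Exponential pattern: r(g) = 0.3 + 0.6 × exp(−g/τ).

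**Formula.** With equal SDs σ, the true variance of a difference is 2σ²(1 − r_ij), and the pooled mean square has expectation σ²(1 − r̄), where r̄ is the mean of the ten correlations. So pooled SE / true SE = √[(1 − r̄)/(1 − r_ij)].

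Example, log pattern 0.9 to 0.3: r̄ = 0.503. Days 0–7: √(0.497/0.1) = 2.23. Days 0–360: √(0.497/0.7) = 0.84.

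**Results** (rates are from 20,000 simulated trials with no true change)

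| Assumed correlation | r̄ | SE ratio 0–7 | SE ratio 0–360 | False positives 0–360 | Familywise error |
|---|---|---|---|---|---|
| Constant 0.6 | 0.600 | 1.00 | 1.00 | 0.6% | 4.8% |
| Log, 0.7 to 0.5 | 0.568 | 1.20 | 0.93 | 1.1% | 5.2% |
| Log, 0.8 to 0.4 | 0.535 | 1.52 | 0.88 | 1.7% | 5.8% |
| Log, 0.9 to 0.3 | 0.503 | 2.23 | 0.84 | 2.2% | 6.4% |
| Exponential, τ = 60 | 0.463 | 1.80 | 0.88 | 1.8% | 6.5% |
| Exponential, τ = 120 | 0.545 | 1.84 | 0.82 | 2.4% | 6.7% |

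Repeat runs moved the 0–360 rates by about 0.1 percentage point and familywise error by up to about 0.3. In all five falling patterns the day 0–7 false-positive rate was about 0.1% or less.

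**Counter-case.** Take constant correlation 0.5 with SD 2.0 at days 0 and 7 and 1.5 afterwards.
- Mean variance is (4 + 4 + 3 × 2.25)/5 = 2.95, mean covariance is 1.4375, and the pooled mean square is 1.5125.
- Days 0–7: √(3.025/4) = 0.87, so the interval is 13% too narrow.
- Days 0–360: √(3.025/3.25) = 0.965, so it is 3.5% too narrow.
- Pairs among days 30, 120 and 360: √(3.025/2.25) = 1.16, so they are too wide.

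**Separate pre-use baseline.** Adding a sixth time point (assumed at day −14) gives first-to-last ratios of 0.92, 0.86 and 0.82 for the three falling log patterns, so the result does not hinge on which early score is the reference.

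**Check of the fix.** With each later visit compared with day 0 using its own paired standard error, the first Holm step (smallest p against 0.05/4) gave familywise error of 3.8–4.7% in every pattern tried.

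**The case against.** The protocol does not say that a pooled error will be used; this is inferred from the standard form of the named test. A SAP that is not shown could set the error term, and with non-normal data the plan moves to Friedman and Dunn, where this point does not arise. That stands, and it makes the point conditional. It does not remove it: the protocol fixes the test by name, and its own schedule makes the assumption behind that test doubtful.

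A reader might infer more than the document supports:

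- **That the direction of error is certain.** It is not. There is no error under constant correlation, and the early part reverses if early visits are noisier.
- **That the long-term contrast has 3 to 6 times too many false positives.** The top of that range (about 3.0–3.8%) comes from letting correlation decay by visit number, which treats a 7-day gap and the 240-day gap from day 120 to day 360 alike. Patterns based on days give about 1.0–2.5%. The 0.6% benchmark is the per-pair rate implied by Tukey under equal correlation, not a level the protocol states; all these rates lie below 5%.
- **That the day 7 comparison is almost untestable.** A low null rejection rate is not low power. For a mean shift of 0.4 of the visit SD, simulated Tukey power for day 0–7 was 0.52–0.83 across two exponential and two visit-number patterns, no worse than for day 0–360 (0.51–0.71). Only when the effect is 0.4 SD of the difference does it fall, to between 0.1% and 35% across the falling patterns against 55% under equal correlation, and it is near zero only under steep decay.
- **That day 0 versus 360 is the study's one key contrast.** Section 2 shows a long-term interest in pain, but section 5 makes orthotic use for at least 6 months the primary endpoint and patient-reported outcomes secondary. No text singles out this pair.

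**Conclusion.** The point holds in conditional form. The named post-test, in its standard form, depends on an equal-variance assumption that visits 7 to 360 days apart make doubtful. If correlation falls with days apart and visit SDs are equal, day 0–360 intervals are about 7–18% too narrow and day 0–7 intervals about 20–120% too wide. Familywise inflation is modest, at about 5–7%; the main harm is uneven precision across individual contrasts. These sizes rest on assumed correlations, complete data and the parametric route being taken.

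**What to change.** In the parametric route, replace pooled-error Tukey with paired contrasts of each later visit against the reference score, each with its own standard error and Holm-adjusted. A mixed model with unstructured covariance for the same contrasts is the alternative. State whether the reference is the pre-use or the day 0 score: day 0 gives four contrasts, a separate pre-use score gives five. There is no need to name a pain contrast as primary, and doing so would conflict with the primary endpoint in section 5.

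The data and visits are unchanged; the cost is analysis wording and work. The downside is that comparisons among later visits become descriptive. For a standardized difference of 0.4 at n = 52, power is 0.62 per contrast at 0.05/4, which is Holm's strictest step. That compares with 0.55 for all-pairs Tukey under equal correlation and 0.81 for a single unadjusted contrast.
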